7.4.4. Primary outcome - model non-convergence

If the mixed-effect logistic regression model with random cluster and cluster-period effects does not converge, we will remove the cluster-period random effects and fit a mixed-effects model with a random effect for cluster.

If this model does not converge, then we will perform a cluster-level analysis weighted by cluster size to ensure we are targeting the participant-level effect [9]. To perform a cluster-level analysis, for each outcome and for each cluster we will calculate a cluster-level summary statistic for the baseline period and for the post-randomisation period separately. The cluster-level summary statistic will be the proportion of the cluster who experience the outcome.

The data will then be transformed from long format to wide format. That is, instead of having two observations per cluster (one observation that describes the summary statistic during the baseline period and one observation that describes the summary statistics during the post-randomisation phase), each cluster will have one row of data.

Relative risk

To obtain a relative risk, we will fit a linear regression model to a transformed cluster-level summary statistic (log transformation) with a fixed effect for allocated exposure to E-MOTIVE and a fixed-effect for baseline summary measure. We will take the exponential of the covariate related to allocated exposure to E-MOTIVE to obtain the relative risk and 95% confidence intervals. We will use the unconditional standard errors to obtain the confidence interval, as this allows for correlation amongst the observations [12].

Risk difference

To obtain the risk difference, a linear regression model will be fitted to the cluster-level proportions with a fixed-effect for allocated exposure to E-MOTIVE and a fixed-effect for baseline summary measure. We will use the unconditional standard errors to obtain the confidence interval, as this allows for correlation amongst the observations [12].

7.5. Analysis methods – secondary outcomes

See Appendix D for information on how variables will be derived for the analysis. A template for reporting the secondary outcomes is given in Appendix E5.

Binary outcomes

All secondary clinical outcomes that are binary will be analysed in the same way as the primary outcome (see section 7.4). In summary, they will be analysed using a mixed-effect logistic regression model, with a random effect for cluster and a random effect for cluster-by-period. The analysis will use a constrained baseline analysis. We will adjust for covariates used in the randomisation process: country (Kenya, Nigeria, South Africa, or Tanzania); Oxytocin quality (high quality or low quality); number of vaginal births (above median or below median); and primary outcome prevalence (above median or below median). Risk ratio and risk differences will be obtained from the logistic model using marginal standardisation. If these models fail to converge, we will remove the cluster-period random effects and fit a mixed-effects model with a random effect for cluster. If this model also fails to converge, an unweighted cluster-level analysis will be performed in the manner described in section 7.4.4.

Continuous outcomes

All secondary clinical outcomes that are continuous will be analysed using a linear mixed-effect model. The analysis will use a constrained baseline analysis, in the same format as the primary outcome. A binary variable will indicate whether observations are taken from the baseline period (0) or the post-randomisation period (1) of the study. A binary 'treatment' variable will indicate whether observations were exposed to the E-MOTIVE intervention. That is, observations taken in the post-randomisation period in clusters allocated to E-MOTIVE will have a value of 1, and all other observations (control clusters and E-MOTIVE clusters during baseline phase) will have a value of 0. This binary treatment variable will be used to determine the impact of the intervention. To allow for correlation of observations within a cluster, a random effect for cluster

7.6. Distributional assumptions and outlying responses

Distributional assumptions (e.g., normality of regression residuals for continuous outcomes) will be assessed visually prior to analysis. In the first instance the proposed primary method of estimation in this analysis plan will be followed. If responses are particularly skewed and/or distributional assumptions violated, the impact of this will be examined through sensitivity analysis; this will consist of transformation of responses prior to analysis (e.g., log transformation) in the first instance.

If extreme values are apparent and considered to be affecting the integrity of the analysis, a sensitivity analysis consisting of removing the outlying response(s) and repeating the analysis will be performed.

Output from these analyses, if performed, will be described, and presented alongside the original analysis (or included, e.g., in appendices) with the excluded values clearly labelled. See section 7.11 for further details regarding sensitivity analyses.

7.7. Handling missing data

In the first instance, analysis will be completed on received data only with every effort made to follow-up patients to minimise any potential for bias. In E-MOTIVE, there is the potential for missing outcome data and missing covariate data, which is described below. A planned sensitivity analysis using multiple imputation to allow for missing data is described in section 7.11.

Missing outcome data

Primary outcome

Only blood loss data that is source verified is included in the primary analysis of the primary outcome. There are two reasons that a woman could have missing outcome data, (i.e., missing source verified blood loss data): 1) woman has blood loss data recorded but it is not source verified; and 2) woman has no blood loss data recorded on the case report form.

Secondary clinical outcomes

Secondary clinical outcomes may contain some missing data. Blood loss outcomes (blood loss 2 hours postpartum and 24 hours postpartum) and primary PPH may contain missing data for the same reason as the primary outcome. Other outcomes may contain missing information if the case report form containing outcome data has not been completed fully.

Secondary Implementation outcomes

For all implementation outcomes, the case report form denotes whether a woman received the outcome in question. It is assumed if it was not denoted as a “yes” on the case report form that the woman did not receive the outcome. As such, there is no missing data for the implementation outcomes.

Missing covariate data

All cluster-level data included in (unadjusted) primary analysis models (country, oxytocin quality, cluster size) will be complete and not contain any missing information. Country is known for each participant based on their cluster. The quality of Oxytocin has been measured and evaluated for all clusters. The cluster size will be based on the number of patients in the cluster during the baseline period.

Individual data included in the (adjusted) sensitivity analysis models (age; parity; multiple pregnancy; mode of birth; and birth weight) may contain missing data.

7.8. Analysis methods – exploratory outcomes and analyses

Not applicable

7.9. Safety data

Analysis of all outcomes including safety outcomes are covered in section 7.10.

7.10. Planned subgroup analyses

We will estimate and report subgroup effects irrespective of their statistical significance. The results of subgroup analyses will be treated with caution. Analysis will be limited to the primary composite outcome and key implementation outcomes only. The planned subgroup analyses are:

- Baseline period PPH rate (above median vs below median) as objectively diagnosed by blood collection drape using data from the baseline period
- Number of vaginal births (using baseline period size) (above median size vs below median size)
- Age (three levels categorised by tertiles of the distribution)
- Parity (none vs any)
- Type of pregnancy (singleton vs multiple),
- Gestational age (term vs preterm),
- Mode of birth (spontaneous vs assisted),
- Presence of any risk factors for PPH vs no risk factors for PPH (Risk factors for PPH are: diagnosis of preeclampsia, induction or augmentation of labour, previous caesarean, previous post-partum haemorrhage, antepartum haemorrhage, episiotomy, vaginal tears, retained placenta)
- Country (Kenya vs Nigeria vs South Africa vs Tanzania).
- Compliance with the bundle (facilities split into above or on median vs below median). Compliance with the MOTIVE bundle is defined as adherence with three core elements of the bundle: administration of oxytocic drugs, TXA and IV fluids. If all three core elements are administered, this will be deemed positive for bundle compliance.
- Time since intervention exposure (exposure (defined as number of months since cluster began post-randomisation phase) (described below)

Time by treatment interaction

To evaluate whether the intervention effect is consistent over time, we will estimate the time by treatment interactions. To do this, we will categorise observations made in the post-randomisation phase to: month 1; month 2; month 3; month 4; month 5; month 6; and month 7.

The analysis of the subgroups will be performed by including a treatment by subgroup interaction parameter in the regression model. Subgroup analyses that are at the cluster level (for example, country) will contain a between-within small sample correction – which is recommended when using mixed models for binary outcomes[15]. For this, we will use the t-

distribution with the appropriate degrees of freedom (number of clusters minus number of parameters estimated in the model).

For each subgroup analysis listed above, we will report the summary measure with 95% confidence interval in each sub-group and the p-value for interaction parameter. We also plan to present the relative measure of differences (ratio of ratios) between subgroup-specific summary measures, along with measures of uncertainty. The “ratio of ratios” will be obtained using post-estimation commands.

All sub-groups are for checking for consistency across various levels of the subgroup.

A template for reporting the subgroup analyses for the primary outcome is given in Appendix E6. These results may be presented as a forest plot to aid interpretability of the results.

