The key secondary implementation outcomes of special interest are 1) PPH detection (with the following numerator and denominator: women who objectively had PPH (source-verified blood loss ≥ 500 mL after weighing the drape) and were diagnosed with PPH by the birth attendants divided by the total number of women who objectively had PPH (source verified blood loss ≥ 500 mL after weighing the drape), and 2) compliance with MOTIVE bundle (with the following numerator and denominator: women who objectively had PPH and were treated with the PPH bundle following a diagnosis of PPH by the birth attendants divided by the total number of women who objectively had PPH (blood loss ≥ 500 mL after weighing of the drape). Compliance with the MOTIVE bundle is defined as adherence to three core elements of the bundle: administration of oxytocic drugs, TXA and IV fluids. If all three core elements are administered when a PPH is diagnosed, this will be deemed positive for bundle compliance. If any of the three core elements are not administered when a PPH is diagnosed, then this will be deemed negative for bundle compliance. It is hypothesised that the causal mechanism underpinning the intervention is that it will increase the rate at which PPH is diagnosed; and that an increase in awareness of women suffering from PPH will subsequently lead to an increase in uptake in the interventions to stop PPH from progressing to severe consequences. This will ultimately lead to a reduction in the proportion of women suffering adverse outcomes from PPH.

Other implementation outcomes are:

1. PPH treatment (with the following numerator and denominator: women diagnosed with PPH by the birth attendants divided by the total of women having a vaginal birth in the health facility)
2. Bundle usage (with the following numerator and denominator: women treated with the PPH bundle following a diagnosis of PPH by the birth attendants divided by the total of women having a vaginal birth in the health facility)
3. Bundle usage for PPH (with the following numerator and denominator: women treated with the PPH bundle following a diagnosis of PPH by the birth attendant divided by the total of women diagnosed with PPH by the birth attendants);
4. Uterine massage;
5. Oxytocin use;
6. Misoprostol use;
7. TXA use;
8. Intravenous fluids use;
9. Examination of the genital tract;
10. Number of women receiving any treatment uterotonic;

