The primary composite outcome (severe PPH, postpartum laparotomy for bleeding, and maternal mortality from bleeding) will be considered significant at the 5% level, and effect sizes and 95% CIs will be reported. Treatment effect measures with confidence intervals will be presented for the individual components of the primary composite (severe PPH, postpartum laparotomy for bleeding, and maternal mortality from bleeding), but it is not expected that there will be sufficient power to make definitive conclusions about any of them.

Results on secondary clinical and implementation outcomes (listed in section 6.2), will be interpreted with caution. To this end, treatment effect measures with confidence intervals will be presented as supporting evidence only.

All analysis will be carried out using Stata.

Subgroup Analyses

Tests for statistical heterogeneity (e.g., by including the treatment group by subgroup interaction parameter in the regression model) will be performed prior to any examination of effect estimate within subgroups. The subgroup analyses will be performed on the primary and key secondary implementation outcomes only.

Planned subgroup analyses include A) *Population subgroups*: age (three levels categorised by tertiles of the distribution), previous birth (none vs any), type of pregnancy (singleton vs multiple), gestational age (term vs preterm), type of birth (e.g. spontaneous versus assisted), risk factors for

PPH (diagnosis of preeclampsia, induction or augmentation of labour, previous caesarean, previous postpartum haemorrhage, antepartum haemorrhage, episiotomy, vaginal tears, retained placenta), baseline period PPH rate (low vs high PPH rate as objectively diagnosed by blood collection drape using data from the baseline period), country, number of vaginal births (above median vs below median as calculated using data from the baseline period); and B) *Intervention subgroups*: compliance with the E-MOTIVE intervention (defined as a minimum of administration of oxytocic drugs, TXA and IV fluids for objectively diagnosed PPHs; over the median and below the median; and time since intervention exposure (defined as number of months since cluster began post-randomisation phase).

Missing Data

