4.2. Trial interventions

Intervention: The E-MOTIVE intervention targets healthcare providers and consists of an implementation strategy for early detection of PPH, which allows the initiation of the 'first response' treatment bundle, which is called MOTIVE, consisting of uterine Massage, Oxytocic drugs, Tranexamic acid, IV fluids and Examination & Escalation (See Protocol, Box 2). The timing, dosing and manner with which these interventions will be implemented will be in line with WHO recommendations and local protocols where available. The implementation strategy focuses on (i) calibrated drape with trigger line, (ii) E-MOTIVE emergency trolley and/or carry case, (iii) simulation-based training on-site with peer-assisted learning, (iv) feedback of actionable data to providers, and (v) local E-MOTIVE champions.

Control: Usual care with dissemination of the current guidelines. In usual care, 'first response' treatment may include some or all of the components of the MOTIVE treatment

bundle. All components are routinely available in all facilities and recommended for all women with PPH, but currently are used inconsistently by healthcare providers.

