14. Use of uterine balloon tamponade postpartum until discharge from the cluster[†];
15. Blood transfusion postpartum until discharge from the cluster^{†*};
16. Blood transfusion for postpartum haemorrhage until discharge from the cluster^{†*};
17. Intensive Care Unit (ICU) admissions postpartum until discharge from the cluster^{†*};
18. Primary severe PPH (defined as blood loss ≥ 1000 ml) following vaginal birth in the cluster measured up to 2 hours postpartum[†];
19. Postpartum laparotomy for bleeding until discharge from the cluster*;
20. Postpartum maternal death from bleeding until discharge from the cluster*;

[†]Combined clinical and quality of care exploratory outcomes where we may observe an increase or a reduction if E-MOTIVE is effective.

*In cases where a woman is transferred to another facility postpartum, discharge from the cluster relates to the facility the woman is transferred to and the relevant outcomes will be obtained from the facility to which the woman was referred.

Secondary Implementation Outcomes

The secondary implementation outcomes are:

1. PPH treatment (with the following numerator and denominator: women diagnosed with PPH by the birth attendants divided by the total of women having a vaginal birth in the health facility);
2. Bundle usage (with the following numerator and denominator: women treated with the PPH bundle following a diagnosis of PPH by the birth attendants divided by the total of women having a vaginal birth in the health facility);
3. Bundle usage for PPH (with the following numerator and denominator: women treated with the PPH bundle following a diagnosis of PPH by the birth attendant divided by the total of women diagnosed with PPH by the birth attendants);
4. Uterine massage;
5. Oxytocin use;
6. Misoprostol use;
7. TXA use;
8. Intravenous fluids use;
9. Examination of the genital tract;
10. Number of women receiving any treatment uterotonic;
11. Number of women requiring additional treatment interventions (not responding to the MOTIVE bundle).

All secondary implementation outcomes will be reported with three denominators:

- The total study population.
- Women diagnosed with PPH by the birth attendant.
- Women who objectively had PPH (blood loss \geq 500 mL after weighing the drape).

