Appendix D: Data manipulations

The Trial Statistician will derive all responses from the raw data recorded in the database.

The following variables will be obtained directly from the raw data – where they are recorded in an appropriate form for analysis:

Cluster demographics

- Country (Kenya, Nigeria, South Africa, Tanzania)
- Number of births (total, caesarean, and vaginal) during study from weekly facility forms
- Number of births contributing to the study from pregnancy outcome forms
- Number of staff (Consultant Obstetrician; Medical Doctor; Clinical Officer; Medical Student; Nurse; Midwife; Nurse Midwife; Nurse/Midwifery student; other healthcare professional) – data is collected monthly, and the average number of staff in each category per month will be collated for each cluster

Individual patient demographics

- Previous births (Numerical)

- Previous caesarean section (Yes or No)
- PPH in previous pregnancy (Yes or No)
- Age (Numerical)
- Index birth
- Multiple pregnancy
- Mode of birth (Spontaneous vaginal or forceps or ventouse)
- Birth weight (Numerical)
- Gestational age at birth (Numerical)
- Antepartum haemorrhage (Yes or No)
- Preeclampsia (Yes or No)
- Labour augmented or induced (Yes or No)
- Retained placenta or manual removal of the placenta (Yes or No)

Primary Outcome Components

- Laparotomy for bleeding (Yes or No)
- Maternal mortality for bleeding (Yes or No)

Secondary/Exploratory Clinical Outcomes

- Laparotomy (Yes or No)
- Laparotomy with compression sutures (Yes or No)
- Laparotomy with arterial ligation (Yes or No)
- Hysterectomy (Yes or No)
- Hysterectomy for bleeding (Yes or No)
- All cause maternal mortality (Yes or No)
- All cause neonatal mortality (Yes or No)
- Non-pneumatic anti-shock garment (NASG) (Yes or No)
- Uterine balloon tamponade (Yes or No)
- Blood transfusion (Yes or No)
- Blood transfusion for bleeding (Yes or No)
- ICU admissions (Yes or No)
- Transfer to higher level cluster (Yes or No)

Secondary/Exploratory Implementation Outcomes

- PPH detection (Yes or No)
- Uterine massage (Yes or No)
- Oxytocin use (Yes or No)
- Misoprostol use (Yes or No)
- Tranexamic acid use (Yes or No)
- Intravenous fluids use (Yes or No)
- Examination of the genital tract (Yes or No)
- Women receiving any treatment uterotonic (Yes or No)
- Women requiring additional treatment interventions (Yes or No)

The following variables will be derived for analysis from the dataset. Details on how they will be derived is presented.

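### The any-risk-factor subgroup includes vaginal tears and retained placenta, which are not fixed before PPH is recognised, so membership could depend on arm and bleeding

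*SAP*

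**What the plan says.** SAP 7.10 plans a subgroup analysis of any versus no PPH risk factor, for the primary outcome and the two key implementation outcomes. The listed factors are preeclampsia, induction or augmentation, previous caesarean, previous PPH, and then "antepartum haemorrhage, episiotomy, vaginal tears, retained placenta". Protocol 11.2 names the same factors, also ending in "episiotomy, vaginal tears, retained placenta", and files them under population subgroups. Neither document limits the list to factors known before PPH is recognised.

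The model works by "including a treatment by subgroup interaction parameter in the regression model". The interaction p-value and the ratio of ratios are reported whatever their significance.

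The bundle in SAP 4.2 includes "Tranexamic acid, IV fluids and Examination & Escalation". SAP 4.6 lists "Examination of the genital tract" as an implementation outcome compared between arms. Protocol 6.2 states the hypothesis that "it will increase the rate at which PPH is diagnosed", with greater use of treatment to follow.

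SAP Appendix D places "Retained placenta or manual removal of the placenta (Yes or No") among patient demographics, and Appendix E3 tabulates it by arm and period. Vaginal tears and episiotomy appear in neither appendix.

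**The concern.** An interaction test on a subgroup is clean when membership is settled before the intervention can influence it. Here membership can be settled afterwards. If PPH is diagnosed more often under E-MOTIVE and diagnosis leads to examination, some women in that arm could have a tear recorded that would have gone unrecorded under usual care. Those women would mostly be bleeding, and so at high risk of the primary outcome.

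Each such woman with no other factor moves from the no-factor group to the any-factor group, and the events move with her. The benefit then looks larger without risk factors and smaller with them, even if it is the same in both. SAP 7.10 says its subgroups are there to check consistency, and this variable could produce inconsistency by itself.

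For PPH detection and bundle compliance the route is shorter. Both denominators are women with objectively measured PPH. Diagnosis can lead to the examination that reveals the tear, so a positive outcome can itself place a woman in the any-factor group.

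**Working it through.** The plan gives no figure for this subgroup. The only inputs from the documents are the planning risks (4% to 3%, so RR 3/4 = 0.75, Protocol synopsis) and the planned size. All recording shares below are assumptions.

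**Check 1: extra recording among severe cases**

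Assume 40% of women have another listed factor and twice the risk of the rest. Assume also that the true RR is 0.75 in everyone and that tears are recorded in 15% of women without other factors. Only the share among intervention-arm severe cases varies. *Severe case* here means a primary-outcome event.

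Control risk r without other factors: 0.6r + 0.4(2r) = 4%, so r = 2.857% and 2r = 5.714%. Under intervention these become 2.143% and 4.286%.

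Per 100,000 control women:
- No other factor: 60,000 women, 1,714 events. Tears move 257 events (15%) and 8,743 non-events (15% of 58,286).
- Any factor: 49,000 women, 2,286 + 257 = 2,543 events, risk 5.190%.
- None: 51,000 women, 1,457 events, risk 2.857%.

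Per 100,000 intervention women there are 1,714 events with other factors and 1,286 without. Tears move 8,807 non-events (15% of 58,714).

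| Tears recorded in severe cases | Any: events / women | RR, any | None: events / women | RR, none | Ratio of ratios |
|---|---|---|---|---|---|
| 15% | 1,907 / 49,000 | 0.75 | 1,093 / 51,000 | 0.75 | 1.00 |
| 20% | 1,971 / 49,064 | 0.774 | 1,029 / 50,936 | 0.707 | 1.10 |
| 30% | 2,100 / 49,193 | 0.823 | 900 / 50,807 | 0.620 | 1.33 |

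A harsher case, with 20% of severe cases in control and 40% under intervention, gives 1.49.

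**Check 2: extra recording among all PPH women**

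Let a share s of women have another factor, with equal baseline risk in both groups. Let a share q of births have PPH, with every primary event among them. A fraction f of exposed-arm PPH women without another factor is newly recorded. For q, Protocol Appendix A implies about 11% to 17% (1,000/8,800 or 1,500/8,800, from 8 × 1,100 women), so 10% to 20% was used.

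Take s = 0.5, q = 0.15, f = 10%. Of 50,000 exposed women with no factor, 750 women and 150 of 1,500 events move.
- None: 1,350/49,250 = 2.741%, RR 0.685.
- Any: 1,650/50,750 = 3.251%, RR 0.813.
- Ratio 1.19.

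For s from 0.3 to 0.7 and q from 0.10 to 0.20:

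| f | False ratio of ratios |
|---|---|
| 2% | 1.02 to 1.06 |
| 5% | 1.06 to 1.16 |
| 10% | 1.13 to 1.33 |
| 20% | 1.28 to 1.72 |

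The planned size is 40 × 192 × 7 = 53,760 post-randomisation births per arm. At s = 0.5 and q = 0.15, a false interaction would be declared about 26% of the time at f = 5% and 75% at f = 10%. These rates are rough: they use binomial standard errors, the post-randomisation period only, and no clustering.

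**Check 3: extra recording unrelated to PPH**

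In the set-up of check 2 the ratio stays at 1.00. In check 1, raising recording to 20% in all intervention women without other factors gives any-factor risk 1,971/52,000 = 3.791% (RR 0.731) and no-factor risk 1,029/48,000 = 2.143% (RR 0.75). The ratio is 0.97, a slight dilution in the other direction. The upward distortion therefore needs the link between recording and bleeding.

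**The case against.** The strongest reply is that the key step is undocumented. Nothing states when or how tears are recorded. If they are noted at routine inspection after every birth in both arms, little or no bias arises. Nor do the documents predict that examination itself will rise. The hypothesis concerns diagnosis and treatment uptake in general, compliance is defined without examination, and usual care may include any bundle component. This stands, and it limits the point to a risk.

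Second, the larger scenarios are hard to support. Protocol 1.1 reports treatment uterotonic use of 26% at 500–600 ml but 70% at 1000–1100 ml in the cited multicountry trial, so the room for improvement narrows with severity. If examination behaved similarly (an analogy only), going from 70% to 100% would raise recording from 15% to about 21% (0.15 × 100/70), a ratio of about 1.12. Doubling goes well beyond that. This stands too.

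Third, a reader might infer that the examination step also uncovers retained placenta. No passage says so. What remains is that the variable is coded together with manual removal, a procedure done after birth. Its frequency by arm and period is already in Appendix E3.

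Fourth, SAP 7.10 says "The results of subgroup analyses will be treated with caution", and this is one of eleven subgroups. General caution guards against reading too much into chance findings. It does not remove a systematic shift from a reported p-value and ratio of ratios.

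**Conclusion.** The point holds as a foreseeable risk to one exploratory subgroup. Because the list contains factors not settled before PPH is recognised, membership could depend on arm and on bleeding, and a uniform effect could appear to differ between the groups. A modest assumed shift (15% to 20% of severe cases without other factors) gives a false ratio of ratios of about 1.10. The 1.33 figure is an upper scenario that rests on doubled recording. If only about 2% of exposed PPH women are reclassified, the ratio is 1.02 to 1.06.

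The case is strongest for vaginal tears and weaker for retained placenta. It is more direct for PPH detection and bundle compliance than for the primary outcome, although no size was calculated there.

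A reader might conclude that the analysis will produce a false interaction, or that the main trial result is in doubt. The documents support neither. The recording process is not described, and the primary analysis does not use this variable. This is a cheap improvement.

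**What to change.** In SAP 7.10, define the main version of this subgroup by preeclampsia, induction or augmentation, previous caesarean, previous PPH, antepartum haemorrhage and episiotomy. Keep the full prespecified list as a supplementary version, labelled as including factors that may be recorded after PPH is recognised. Add vaginal tears to the Appendix E3 table by arm and period, so that any differential recording can be seen; retained placenta is already there. A line in Appendix D saying how and when tears and episiotomy are recorded would let readers judge the risk.

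The cost is SAP wording and one table row, using variables the subgroup already needs. The downside is that two recognised risk factors leave the main version of this one subgroup.
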